### **2.1.1 General definitions**

#### **Study treatment**

In this and subsequent analysis plan module (TFL and PDS), the terms “investigational drug”, “study drug” and “study treatment” refers to deferasirox FCT as well as deferasirox DT.

#### **Study treatment start and end date**

Study treatment start date is defined as the first date when a non-zero dose of study drug is administered and recorded on the Drug Administration Record (DAR) CRF page. Similarly, study drug end date is defined as the last date when a non-zero dose of study drug is administered and recorded on the DAR CRF page of the study.

#### **End of study**

The end of study is defined as the earliest occurrence of one of the following:

- The patient has reached Week 96 at Extension phase.
- Deferasirox FCT is locally reimbursed for this indication (only applicable in Extension phase)
- Another clinical study or post-trial access program becomes available that can continue to provide deferasirox FCT in this patient population and all patients ongoing are eligible to be transferred to that clinical study

The investigator will be responsible for informing IRBs and/or EC.

### **Patient completed**

A patient is considered as having “completed the study” if the patient has completed the core phase of the study, i.e. Week 48.

### **Study day**

Study day will be calculated as (event date – study drug start date + 1 day) for events that occurred on or after study drug start date (e.g. visit, lab samples, AEs). For events prior to study drug start date (e.g. time of diagnosis), study day will be negative and calculated as (event date – study drug start date). Note that study drug start date is study day 1 and the day before study drug start date is study day -1 (i.e. no study day 0).

Due to the study drug dosing schedule, one month will be considered as 28 days. However, for “time since event” data (e.g. medical history), one month will be considered as 365.25/12 days for events that occurred prior to study Day 1. Time from events prior to the start of study drug, e.g., time since diagnosis, is calculated as the difference between the start date of study drug and the date of prior event.

Note that, the first dose day is Day 1, and the day before the first dose day is counted as Day -1 (not Day 0).

### **Baseline assessment:**

Baseline assessment in general will be defined as the last assessment prior to the start of the study treatment which is the assessment taken at Day 1 of study. A baseline value refers to the last measurement made prior to administration of first dose of study treatment.

### **Post baseline assessment:**

A post-baseline value refers to a measurement taken after the first dose of study treatment.

### **Treatment period**

The planned treatment duration of the core phase is 48 weeks (24 weeks of DT followed by 24 weeks of FCT) and the planned treatment period for the extension phase is another 48 weeks of FCT.

The total duration of the study is approximately 104 weeks (including the Screening, Treatment and Safety Follow-up visits).

Patients will be followed up for safety purposes for 30 days after the last dose of study drug (regardless if that situation occurs during core or extension phase).

### **Lost to follow up**

The patients whose study completion status is unclear because they fail to appear for study visits without stating an intention to withdraw.

### **Visit window**

Visit wise following window period will be used:

Visit 3 Date of visit should be 14 days from Visit 2 also consider buffer +/-2 days (e.g. Timeframe to do the visit is 12 days to 16 days)

Visit 4 Date of visit should be 28 days from Visit 2 also consider buffer +/-2 days (e.g. Timeframe to do the visit is 26 days to 30 days)

Visit 5 Date of visit should be 56 days from Visit 2 also consider buffer +/-2 days (e.g. Timeframe to do the visit is 54 days to 58 days)

Visit 6 Date of visit should be 84 days from Visit 2 also consider buffer +/-2 days (e.g. Timeframe to do the visit is 82 days to 86 days)

Visit 7 Date of visit should be 112 days from Visit 2 also consider buffer +/-2 days (e.g. Timeframe to do the visit is 110 days to 114 days)

Visit 8 Date of visit should be 140 days from Visit 2 also consider buffer +/-7 days (e.g. Timeframe to do the visit is 133 days to 147 days)

Visit 9 Date of visit should be 168 days from Visit 2 also consider buffer +/-7 days (e.g. Timeframe to do the visit is 161 days to 175 days)

Visit 10 Date of visit should be 196 days from Visit 2 also consider buffer +/-7 days (e.g. Timeframe to do the visit is 189 days to 203 days)

Visit 11 Date of visit should be 224 days from Visit 2 also consider buffer +/-7 days (e.g. Timeframe to do the visit is 217 days to 231 days)

Visit 12 Date of visit should be 252 days from Visit 2 also consider buffer +/-7 days (e.g. Timeframe to do the visit is 245 days to 259 days)

Visit 13 Date of visit should be 280 days from Visit 2 also consider buffer +/-7 days (e.g. Timeframe to do the visit is 273 days to 287 days)

Visit 14 Date of visit should be 308 days from Visit 2 also consider buffer +/-7 days (e.g. Timeframe to do the visit is 301 days to 315 days)

Visit 15 Date of visit should be 336 days from Visit 2 also consider buffer +/-7 days (e.g. Timeframe to do the visit is 329 days to 343 days)

Visit 16 Date of visit should be 364 days from Visit 2 also consider buffer +/-7 days (e.g. Timeframe to do the visit is 357 days to 371 days)

Visit 17 Date of visit should be 392 days from Visit 2 also consider buffer +/-7 days (e.g. Timeframe to do the visit is 385 days to 399 days)

Visit 18 Date of visit should be 420 days from Visit 2 also consider buffer +/-7 days (e.g. Timeframe to do the visit is 413 days to 427 days)

Visit 19 Date of visit should be 448 days from Visit 2 also consider buffer +/-7 days (e.g. Timeframe to do the visit is 441 days to 455 days)

Visit 20 Date of visit should be 476 days from Visit 2 also consider buffer +/-7 days (e.g. Timeframe to do the visit is 469 days to 483 days)

Visit 21 Date of visit should be 504 days from Visit 2 also consider buffer +/-7 days (e.g. Timeframe to do the visit is 497 days to 511 days)

Visit 22 Date of visit should be 532 days from Visit 2 also consider buffer +/-7 days (e.g. Timeframe to do the visit is 525 days to 539 days)

Visit 23 Date of visit should be 560 days from Visit 2 also consider buffer +/-7 days (e.g. Timeframe to do the visit is 553 days to 567 days)

Visit 24 Date of visit should be 588 days from Visit 2 also consider buffer +/-7 days (e.g. Timeframe to do the visit is 581 days to 595 days)

Visit 25 Date of visit should be 616 days from Visit 2 also consider buffer +/-7 days (e.g. Timeframe to do the visit is 609 days to 623 days)

Visit 26 Date of visit should be 644 days from Visit 2 also consider buffer +/-7 days (e.g. Timeframe to do the visit is 637 days to 651 days)

Visit 777 Date of visit should be 672 days from Visit 2 also consider buffer +/-7 days (e.g. Timeframe to do the visit is 665 days to 679 days)

## 2.2 Analysis sets

The following analysis sets will be used in this study.

**Enrolled Set:** The Enrolled Set comprises all patients enrolled in this study. Patients who discontinued from the study due to ineligibility immediately after Visit 2 are not considered as enrolled.

**Full Analysis Set (FAS):** The Full Analysis Set comprises all patients to whom study treatment has been assigned and who received at least one dose of each study treatment (DT and FCT). Patients will be analyzed according to the treatment they have been assigned to.

**Safety Set (SAF):** The Safety Set includes all patients who received at least one dose of either study treatment (DT or FCT), and at least one safety assessment on or after Day 1.

Patients will be analyzed according to the study treatment received, where treatment received is defined as the assigned treatment if the patient took at least one dose of that treatment or the first treatment received if the assigned treatment was never received.

**Per-Protocol Set (PPS):** The Per-Protocol Set consists of a subset of the patients in FAS who are compliant with requirements of the clinical study protocol (CSP) without any major protocol deviation.

Any major protocol deviation will lead to exclusion of patients from PPS. The list of PDs is defined in [Section 5.5](#).

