Table 14-18	Patients pre-treated with Deferoxamine.....	95

List of abbreviations

AE	Adverse Event
AML	Acute Myeloid Leukemia
ALT	Alanine aminotransferase/glutamic pyruvic transaminase/GPT
AST	Aspartate aminotransferase/glutamic oxaloacetic transaminase/GOT
AUClast	The AUC from time zero to the last measurable concentration sampling time (tlast) (mass x time x volume-1) after single dose
AUCtau	The AUC calculated to the end of a dosing interval (tau) at steady-state (amount x time x volume-1)
b.i.d.	bis in diem/twice a day
C2hr	Post-dose 2 hr plasma concentration
Cmax	The maximum (peak) observed plasma, blood, serum, or other body fluid drug concentration after single dose administration (mass x volume-1)
CRO	Contract Research Organization
Ctrough	Pre-dose plasma concentration
CSR	Clinical study report
DFO	Deferoxamine
DFP	Deferiprone
DS&E	Drug Safety and Epidemiology
DT	Dispersible Tablet
eCRF	Electronic Case Report/Record Form
ECG	Electrocardiogram
EOS	End Of Study
i.v.	intravenous(ly)
FAS	Full Analysis Set
FCT	Film-coated tablet
GI	Gastrointestinal
ICH	International Conference on Harmonization
ICT	Iron chelation therapy
IEC	Independent Ethics Committee
IO	Iron Overload
IPSS-R	Revised International Prognostic Scoring System
IRB	Institutional Review Board
IRT	Interactive Response Technology that includes Interactive Voice Response System and Interactive Web Response System
LC-MS/MS	Liquid Chromatography-Mass Spectrometry/Mass Spectrometry
LIC	Liver Iron Concentration
MDS	Myelodysplastic syndrome
o.d.	omnia die /once a day
NCCN	National Comprehensive Cancer Network
NOAELs	No-adverse-effect-levels
PAS	PK Anaylisis Set
p.o.	per os /by mouth/orally
PHI	Protected Health Information

[figure not shown]
PRO	Patient Reported Outcome
RAP	The Report and Analysis Plan (RAP) is a regulatory document which provides evidence of preplanned analyses
RBC	Red Blood Cell
REB	Research Ethics Board
SAE	Serious Adverse Event
SEC	Study Evaluation Completion
SOP	Standard Operating Procedure
QoL	Quality of Life
VES	Visit Evaluation Schedule

Glossary of terms

Assessment	A procedure used to generate data required by the study
Dose level	The dose of drug given to the patient (total daily or weekly etc.).
Enrollment	Point/time of patient entry into the study; the point at which informed consent must be obtained (i.e. prior to starting any of the procedures described in the protocol)

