6.1.1 Dosing regimen

Having completed the screening period (including the 5-day wash-out period for patients previously treated with Deferiprone/DFP or Deferoxamine/DFO), eligible patients will start the core phase and be switched on the Day 1 visit to deferasirox DT for 24 weeks followed by deferasirox FCT for 24 weeks duration. Upon completion of Week 48 (Core Phase), the patient can still be treated with deferasirox FCT for a maximum of another 48 weeks or until one of the end of study criteria defined is met, whichever comes first.

The starting dose on Baseline Day 1 would be as following:

- Deferasirox DT of 20 mg/kg/day in transfusion-dependent thalassemia (TDT)
- Deferasirox DT of 10 mg/kg/day in non- transfusion-dependent thalassemia (NTDT),

Table 6-1 Equivalent FCT starting dose at Week 25

Equivalent dose to be used	
Deferasirox DT (mg/kg/day)	Deferasirox FCT (mg/kg/day)
5	3.5
10	7
15	10.5
20	14
25	17.5
30	21

Equivalent dose to be used	
Deferasirox DT (mg/kg/day)	Deferasirox FCT (mg/kg/day)
35	24.5
40	28

All iron chelation pre-treated patients who had received treatment with deferoxamine (DFO) and deferiprone (DFP) will be initiated on deferasirox DT. The dose of deferiprone will be determined by their serum ferritin and the dose of deferoxamine by using the equivalent deferasirox DT dose (see [Appendix 14.2](#)).

Dose adjustment for better treatment effects, based on serum ferritin levels and investigator's judgment, will be allowed for ICT naïve patients after 4 weeks of study treatment and for ICT pre-treated patients every 3 months. The dose adjustments will be performed in steps of 5-10 mg/kg/day for deferasirox DT or in steps of 3.5-7 mg/kg/day for deferasirox FCT.

For each patient the daily dose is calculated by the physician based on the patient's actual body weight, and then rounded up or down to the nearest whole tablet according to the available strengths of deferasirox tablets (125 mg, 250 mg and 500 mg for the DT and 90 mg, 180 mg and 360 mg for the FCT, see [Appendix 14.1](#)).

The investigator should instruct the patient (or legal patient's representative in the case of pediatric patients) to take the study drug as prescribed. All doses planned and prescribed to the patient and all dose changes including reasons for change during the study must be recorded in the eCRF.

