7.1.1.2 Information to be collected on screening failures

Patients who sign an informed consent but fail to be started on treatment for any reason will be considered a screen failure. The reason for not being started on treatment will be entered on the Screening Log.

The demographic information, informed consent, inclusion/exclusion evaluation and Screening log pages in the eCRF must also be completed for Screen Failure patients. No other data will be entered into the clinical database for patients who are screen failures, unless the patient experienced a Serious Adverse Event (SAE) during the Screening Phase (see [Section 8](#) for SAE reporting details).

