7.1.3.1 Criteria for premature patient withdrawal

Patients may voluntarily withdraw from the study or be dropped from it at the discretion of the investigator/Sponsor at any time. Patients may be withdrawn from the study if any of the following occur unless the investigator decides in the best interest of the patient to switch from deferasirox DT to deferasirox FCT:

- Pregnancy (not applicable for the switch)
- Unwillingness to comply with procedures as outlined in the study protocol, including unwillingness to comply with the prescribed study treatment
- Discovery of patient ineligibility (not applicable for the switch)
- Intake of prohibited medications (not applicable for the switch)
- Adverse event(s)
- Abnormal lab value(s)

- Unsatisfactory therapeutic effect
- Protocol violation (not applicable for the switch)
- Subject withdrew consent (not applicable for the switch)
- Lost to follow-up (not applicable for the switch)
- Administrative problems (not applicable for the switch)
- Death (not applicable for the switch)
- Decision of the Sponsor
- Unacceptable toxicity in the opinion of the investigator/Sponsor

If such withdrawal occurs, or if the patient fails to return for visits, the investigator must determine the primary reason for a patient's premature withdrawal from the study and record this information on the Study Evaluation Completion eCRF.

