10.1 Analysis sets

The following analysis sets will be used in this trial.

Enrolled Set

The Enrolled Set comprises of all patients enrolled in this study.

Full Analysis Set

The Full Analysis Set (FAS) comprises all patients to whom study treatment has been assigned and who received at least one dose of each study treatment (DT and FCT). Patients will be analyzed according to the treatment they have been assigned to.

Safety set

The Safety Set includes all patients who received at least one dose of either study treatment (DT or FCT), and at least one safety assessment on or after Day 1.

Patients will be analyzed according to the study treatment received, where treatment received is defined as the assigned treatment if the patient took at least one dose of that treatment or the first treatment received if the assigned treatment was never received.

Per-Protocol set

The Per-Protocol Set (PPS) consists of a subset of the patients in the FAS who are compliant with requirements of the CSP (clinical study protocol) without any major protocol deviation.

The major protocol deviations that will lead to exclusion of patients from the PPS will be detailed in the SAP.

Pharmacokinetic analysis set

Not applicable

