### **2.3.1 Patient disposition**

The Enrolled Set will be used for the summary and listing of patient disposition. The overall number and percentage of patients who were screened, completed (core phase, extension phase) and discontinued the study (core phase or extension phase) along with reasons for discontinuation will be summarized.

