| E06a                | Hepatitis B or Hepatitis C tests were not performed at visit 1.  | INCLUDE IN EVERYTHING        | 0                    |
| E07                 | Clinical or laboratory evidence of active Hepatitis B or C at visit 1.   | EXCLUDED FROM PPS            | 4                    |
| E08                 | Known history of HIV seropositivity (Elisa or Western blot).   | EXCLUDED FROM PPS            | 4                    |
| E9                  | History of malignancy of any organ system, treated or untreated, within the past 5 years (protocol section 5.3)  | EXCLUDED FROM PPS            | 4                    |
| E10                 | Patients participating in another clinical trial or receiving an investigational drug.   | EXCLUDE FROM FAS             | 1                    |
| E11                 | History of hypersensitivity to any of the study drugs or their excipients  | EXCLUDED FROM PPS            | 4                    |
| E12                 | Significant medical condition interfering with the ability to take part in this study  | EXCLUDE FROM PPS             | 4                    |
| E13                 | Female of child bearing potential unwilling to use contraception as requested by the protocol  | INCLUDE IN EVERYTHING        | 0                    |
| E14                 | Female not meeting post-menopausal criteria stated in the protocol and not using the contraception methods requested in the protocol   | INCLUDE IN EVERYTHING        | 0                    |
| E15                 | Female of child bearing potential with a positive serum pregnancy in the screening visit however subject is enrolled into the study  | EXCLUDE FROM PPS             | 4                    |
| E16                 | Sexually active males not using condom during intercourse while taking drug and for 28 days after stopping study medication  | INCLUDE IN EVERYTHING        | 0                    |
| E17                 | Patients with psychiatric or addictive disorders preventing from giving informed consent or undergoing any of the treatment options or unable or unwilling to comply with the protocol | EXCLUDE FROM FAS AND SAF     | 3                    |

| Deviation ID | Description of Deviation   | Exclusion in Analyses | Severity code |
|---------------------|---|------------------------------|----------------------|

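### The SAP's Enrolled Set carve-out after Visit 2 is not limited to undosed patients, so the Safety Set is not guaranteed to lie within the Enrolled Set; deviation code E17 separately conflicts with the Safety Set definition

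*SAP*

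**What the plan says.** Protocol 10.1 gives the Enrolled Set no exceptions: "The Enrolled Set comprises of all patients enrolled in this study". SAP 2.2 repeats this and adds "Patients who discontinued from the study due to ineligibility immediately after Visit 2 are not considered as enrolled". The SAP's document history dates that change to amendment 1.1 of 4 September 2020, before the interim database lock. SAP section 4 declares no change to protocol-specified analyses.

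The Enrolled Set is the basis for disposition ("The Enrolled Set will be used for the summary and listing of patient disposition", SAP 2.3.1), demographics (2.3.2) and baseline characteristics (2.3.3). The Safety Set requires one dose of either formulation and one safety assessment on or after Day 1. It does not require membership of the Enrolled Set.

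On timing, protocol 6.1.1 has eligible patients "be switched on the Day 1 visit to deferasirox DT for 24 weeks", and Table 7-1 marks administration and dispensing of dispersible tablets at Visit 2. On patients who never start, protocol 7.1.1.2 says "Patients who sign an informed consent but fail to be started on treatment for any reason will be considered a screen failure". On ineligibility found later, protocol 7.1.3.1 lists it among the reasons for premature withdrawal.

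SAP 5.5 Table 1 gives code 3 (out of both the FAS and the Safety Set) to deviation E17, which reads in part "Patients with psychiatric or addictive disorders preventing from giving informed consent or undergoing any of the treatment options or unable or unwilling to comply".

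**The concern.** A disposition table should account for everyone who took study drug. The carve-out turns on when the patient left and why, not on whether a dose was taken, and the SAP sets no time limit for *immediately*. A patient who takes the first dose at Visit 2 and is then withdrawn as ineligible is not a screen failure, because treatment was started, and is not enrolled under the SAP. That patient would have safety data but no line in the disposition or baseline tables, and the discontinuation rate and the count of ineligibility withdrawals would both be too low. A patient with the same eligibility failure found some weeks later would stay enrolled and carry a deviation code.

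E17 works in the other direction. It takes a dosed patient's adverse events out of the Safety Set summaries for a reason that the set's definition does not contain.

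**Working it through.** **No plan figure rests on this rule.** The only number used is the planned enrolment. It reproduces from the sample-size assumptions (45% versus 25%, so discordance 0.70 and difference 0.20; two-sided 5%, 80% power): (1.960 + 0.842)² × (0.70 − 0.20²) / 0.20² = 129.5, rounded up to 130; then 130 / 0.9 = 144.4, rounded up to 145. Nothing below changes it.

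**Set membership.** Crossing dosed yes/no with withdrawn as ineligible straight after Visit 2 yes/no gives:

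| Dosed | Withdrawn as ineligible after Visit 2 | SAP Enrolled Set | Safety Set | Consistent? |
|---|---|---|---|---|
| No | No | in | out | yes |
| No | Yes | out | out | yes; already a screen failure under protocol 7.1.1.2 |
| Yes | No | in | in | yes |
| Yes | Yes | out | in | **no** |

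Visit 2 itself schedules safety assessments on Day 1, so a patient dosed there would normally meet the second Safety Set condition. The deviation table does not remove such patients either. Most eligibility failures carry code 4 (per-protocol set only), and the ferritin failures I05 and I06 carry code 0 (included everywhere). Only codes 2, 3 and 6 remove a patient from the Safety Set.

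**Size.** Let k be the number of dosed patients carved out and D the true number of discontinuations among 145. The documents give neither; both are assumptions here.

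- Rate with everyone counted: D/145.
- Rate under the carve-out: (D − k)/(145 − k).
- Difference: k(145 − D) / [145(145 − k)].

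With D = 20:

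- k = 0: no difference.
- k = 1: 125 / (145 × 144) = 0.6 points.
- k = 2: 250 / (145 × 143) = 1.2 points.
- k = 5: 625 / (145 × 140) = 3.1 points (13.8% against 10.7%).

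With k = 5 and all 145 dosed and assessed, the Safety Set would be 145 and the Enrolled Set 140.

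**Primary analysis.** The FAS requires a dose of both formulations. A patient withdrawn straight after Visit 2 has not reached the film-coated tablet, so the carve-out cannot change the FAS.

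**E17.** The Safety Set is defined by a dose plus an assessment. Code 3 overrides that definition for a dosed patient who is only non-compliant. Missing consent has its own entries, I01a and I01b, also with code 3, so the non-compliance part of E17 is not needed to deal with missing consent.

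**The case against.** The best defence is that the protocol tries to prevent the problem case. Eligibility must be reviewed before any treatment (5.3, 7.1.1.1) and is verified again at Day 1 before drug is given (7.1.1.3). On that view the SAP sentence describes patients who failed the Visit 2 check and were never dosed. The protocol also uses *enrolled* in two ways. The glossary puts enrolment at consent ("the point at which informed consent must be obtained"), whereas 7.1.1.3, 7.1.2 and 7.2.2.7.1 use the word for a step that follows eligibility, and on that usage leaving out an ineligible patient is natural.

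Both points stand as mitigation. They do not justify the wording. If every affected patient was undosed, 7.1.1.2 already classes them as screen failures and the sentence is redundant. The plan also allows for ineligibility being found after the start, through the withdrawal reason in 7.1.3.1 and the deviation codes.

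Three stronger readings are tempting, and the documents do not support them:

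- A reader might infer that dosed patients were in fact removed, because the change log says the definition was altered to reflect the actual situation. That phrase says nothing about dosing.
- A reader might infer that results drove the edit, because the study is open-label. The change predates the interim lock, and nothing points to such a motive.
- A reader might put the effect of five patients at 5/145 = 3.4 points. That ignores the shrinking denominator.

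On E17, the objection that it also covers patients who could not give informed consent is sound. Recoding the whole entry would go too far.

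**Conclusion.** The defect is in the definition. SAP 2.2 does not guarantee that the Safety Set lies within the Enrolled Set, and it would leave a dosed patient withdrawn as ineligible straight after Visit 2 out of the disposition, demographic and baseline tables. It departs from protocol 10.1 without a note in SAP section 4. The effect is confined to descriptive tables and may concern no patient. The 3.1 points rest on the assumed k = 5, D = 20 and a base of 145.

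The E17 conflict is separate and also unquantified. It holds for dosed patients with valid consent who were only unable or unwilling to comply, and not for those who could not consent.

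**What to change.** 1. In SAP 2.2, limit the carve-out to patients who took no study drug. Deleting the sentence would also remove the conflict, but read with the glossary's enrolment at consent it would bring every consented screen failure into the set. Limiting is enough and is the cleaner choice.
2. In SAP 2.3.1, report ineligibility withdrawals at or after Visit 2 under the protocol's reason of discovered ineligibility, with dosed and undosed counts.
3. Split E17. Leave the part on inability to consent as it is, and recode the non-compliance part so that dosed patients with valid consent stay in the Safety Set. Code 1, for example, would do this and leave the current FAS exclusion unchanged.
4. Record any remaining departure from protocol 10.1 in SAP section 4.

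The cost is SAP wording and a rerun of the disposition, demographic and baseline tables, plus the safety tables if any E17 patient was dosed. The discontinuation and deviation counts may look slightly less favourable.
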